16.6.5. Pharmacokinetic

N/A.

16.6.6. Health Outcomes

HIVTSQs
CCI - This section contained Clinical Outcome Assessment data collection questionnaires or indices, which are protected by third party copyright laws and therefore have been excluded.
Treatment Satisfaction Score

 • Total Treatment Satisfaction Score is computed with items 1-11. Items 1-11 are summed to produce a score with a possible range of 0 to 66. • Item 12 will not be included in Total Treatment Satisfaction Score. Instead, it will be treated as a stand-alone item only. • Higher scores represent greater treatment satisfaction as compared to the past few weeks. • A maximum of 5 items can be missing, which can be imputed to reflect the mean of the completed item scores. If 6 or more items are missing, then the treatment satisfaction scale score should not be computed.
Individual Item Scores

 • Items are rated as 6 CCI • Higher scores represent greater satisfaction with each aspect of treatment • For individual item scores outputs, missing scores will not be computed (according to Page

7 of the [HIVTSQ User Guidelines, 2016]).

HIVTSQc

CCI - This section contained Clinical Outcome Assessment data collection questionnaires or indices, which are protected by third party copyright laws and therefore have been excluded.

Treatment Satisfaction Score (Change)

- Total Treatment Satisfaction Score is computed with items 1-11. Items 1-11 are summed to produce a score with a possible range of -33 to 33
- Item 12 will be computed as an individual item only.
- The higher the score, the greater the improvement in satisfaction with treatment; the lower the score, the greater the deterioration in satisfaction with treatment. A score of 0 represents CCI
- A maximum of 5 items can be missing, the missing scores will be imputed with the mean of the completed item scores. If 6 or more items are missing, then the overall treatment satisfaction scale score should not be computed and will remain missing.

Individual Treatment Change Item Scores

- Items are rated as +3 CCI to -3 CCI
- The higher the score, the greater the improvement in satisfaction with each aspect of treatment and the lower the score, the greater the deterioration in satisfaction with each aspect of treatment.

PIN

CCI - This section contained Clinical Outcome Assessment data collection questionnaires or indices, which are protected by third party copyright laws and therefore have been excluded.

CCI - This section contained Clinical Outcome Assessment data collection questionnaires or indices, which are protected by third party copyright laws and therefore have been excluded.

Dimension Score (Chevat, 2008)

- Domains and Clusters
 - Bother from injection site reactions: items 3, 4, 5, 6, 7, 8
 - Leg movement: items 11, 12, 15, 16
 - Sleep: items 9, 10, 13, 14
 - Acceptability: items 17, 18
- 5 items not included in any of these domains and maintained as individual items (items 1, 2, 19, 20, 21) CCI [REDACTED]
- No overall score is calculated per the guidance
- The score of a domain is calculated as the mean of all items with the domain. Higher scores represent worse perception of injection.
- A maximum of <50% items can be missing within a domain, which can be imputed to reflect the mean of the completed item scores within the domain. Thus, if the number of missing items is ≥ 3 CCI [REDACTED] ≥ 2 CCI [REDACTED] ≥ 1 CCI [REDACTED], then the total score for the domain should not be computed.

Individual Item Scores

- Items are rated on a 5-point scale, ranging from 1 CCI [REDACTED] to 5 CCI [REDACTED]

[figure not shown]
- Lower scores represent worse perception of injection
- For individual item scores outputs, missing scores will not be computed.

CCI - This section contained Clinical Outcome Assessment data collection questionnaires or indices, which are protected by third party copyright laws and therefore have been excluded.

CCI

CCI

16.6.7. Viral Genotype and Phenotype

Genotype	
Amino Acid Changes	

 A mutation is considered present whenever the encoded amino acid residue differs from the amino acid that would have been encoded by the wild-type (e.g., HXB2, NL43) comparator gene; e.g., Q148K. If the encoded amino acid is seen as a mixture of wild-type and mutant amino acid, e.g., Q148Q/K, the mutated amino acid is considered present at the codon of interest. If the encoded amino acid is seen as a mixture of two or more amino acids, which may or may not include wild type, e.g., Q184K/H or Q184K/H/Q, etc., for the purposes of calculating the number of mutated amino acids, only one mutation is considered to be present at the codon of interest. 	
Representation of Amino Acid Changes	
Mutations	Amino acid change
T69S	Single mutation from amino acid 'T' (vendor reference) to 'S' (sample) at codon '69'
Q148H/K/R	Mixture of amino acid mutations 'H', 'K' and 'R' (sample) from amino acid 'Q' (vendor reference) at codon '148'
_69_1T	First insertion of amino acid 'T' (sample) at codon '69'
_69_2S	Second insertion of amino acid 'S' (sample) at codon '69'
_69_3S/A	Third insertion of a mixture of amino acids 'S' and 'A' (sample) at codon '69'
L74L/-	Mixture of amino acid 'L' (sample) and a deletion at codon '74'
V75-	Single deletion of amino acid (sample) at codon '75'
Resistance Associated Mutations	

 Known INI mutations associated with the development of resistance to BIC, RAL, EVG, CAB or DTG: 	
Amino Acids in HIV Integrase for Analysis	H51Y, T66A/I/K, E92Q/V/G, Q95K, T97A, G118R, F121C/Y, E138A/K/T, G140A/C/R/S, Y143C/H/R/K/S/G/A, P145S, Q146P, S147G, Q148H/K/R/N, V151L/A, S153F/Y, N155H/S/T, E157Q, G163R/K, S230R, D232N, R263K, L68V/I*, L74I/M*, E138D*, V151I*, G193E*
Notes:	

- Draft listing; may be modified in case of additional substantive data availability.
- INI mutations listed taken from Stanford HIV Resistance Database (http://hivdb.stanford.edu/DR/cgi-bin/rules_scores_hivdb.cgi?class=INI cited 22Feb2021)
- INI substitutions listed above in bold had a score of =60.
*Denotes additional INI mutations added as they were identified during in vitro passage of DTG or seen in a previous DTG study in INI-experienced subjects (ING112574).
- Major resistance mutations to other classes (i.e., NRTI, NNRTI, PI) as defined by the International Antiviral Society-USA (IAS-USA). The most up to date IAS-USA guidelines available at the time of DBF will be used in the analysis [[Wensing, 2019](#)].

Class	Mutations
NRTIs	M41L, A62V, K65R/E/N, D67N, 69 insert, K70E/R, L74V, V75I, F77L, Y115F, F116Y, Q151M, M184V/I, L210W, T215Y/F, K219Q/E
NNRTIs	L100I, K101E/P, K103N/S, V106A/M, V108I, E138A/G/K/Q/R, V179L, Y181C/I/V, Y188C/L/H, G190S/A, H221Y, P225H, F227C, M230I/L,
PIs	D30N,V32I , M46I/L, I47A/V, G48V, I50V/L, I54M/L/V, Q58E, T74P, L76V, V82A/T/F/L/S, N83D, I84V, N88S,L90M

Note: List generated from IAS_USA Guideline, [[Wensing, 2019](#)]

- The pre-specified INI Mutations are identified as below:
 - Per the IAS-USA list of mutations (both minor and major) associated with resistance to Bictegravir, Cabotegravir, Dolutegravir, Elvitegravir, or Raltegravir (IAS-USA 2019 resistance mutations update volume 27 issue 3, 2019): T66A/I/K, L74M, E92Q/G, T97A, G118R, F121Y, E138A/K/T, G140A/C/R/S, Y143C/H/R, S147G, Q148H/K/R, S153F/Y, N155H, R263K
 - Observed mutations during in vitro passage of DTG or seen in a previous DTG study in INI-experienced subjects (study ING112574): H51Y, L74I, L68V/I, E92V, Q95K, E138D, Y143K/S/G/A, P145S, Q146P, V151I/L/A, N155S/T, E157Q, G163R/K, G193E, S230R
 - Mutations per FDA request for Study 201584: Q146L, T124A
- The NNRTI resistance associated mutations (RAMs) are identified per IAS-USA NNRTI mutations (IAS-USA 2019 resistance mutations update volume 27 issue 3, 2019):
 - V90I, A98G, L100I, K101E/H/P, K103N/S, V106A/I/M/T, V108I, E138A/G/K/Q/R, V179D/F/L/T, Y181C/I/V, Y188C/H/L, G190A/E/S, H221Y, P225H, F227C/L/R, M230I/L, L234I
- The RPV RAMs are identified per IAS-USA NNRTI mutations (IAS-USA 2019 resistance mutations update volume 27 issue 3, 2019):
 - L100I, K101E/P, E138A/G/K/Q/R, V179L, Y181C/I/V, Y188L, H221Y, F227C, M230I/L
- The NRTI major mutations associated with resistance to BIKTARVY (Emtricitabine and Tenofovir, IAS-USA 2019 resistance mutations update volume 27 issue 3, 2019):
 - K65R/E/N, K70E, M184V/I

Phenotype

Phenotypic Susceptibility

- Phenotypic susceptibility to all licensed antiretroviral drugs and CAB will be determined using PhenoSense HIV assays from Monogram Inc. and will be reported as fold change (FC) in IC50

relative to wild-type control virus NL4-3, i.e., FC of sample virus = IC50 of sample virus/IC50 of control virus.

- Since the maximum assay limit for FC for each ART varies from assay to assay, FC values that are greater than the maximum assay limit (e.g., '>100') will be interpreted as having a value equal to the smallest maximum assay limit for that ART in the study population for data analysis. Censored values will be presented 'as is' in the listings. Phenotypic susceptibilities will be categorised according to FC as shown in Table below (based on Monogram PhenoSense assay). Clinical cutoffs (where available) or biological cutoffs by PhenoSense will be used to define the phenotypic susceptibility of background treatment by Monogram. PHENOTYP dataset from Monogram contains the phenotypic susceptibility information derived from the cutoff listed below. Thus, phenotypic susceptibility (i.e. full sensitivity and partial sensitivity) will not be re-derived in our analysis.
- Replication capacity is generated as part of standard phenotypic assays

PhenoSense Algorithm

Drug	Abbreviation	Class	PhenoSense cutoff
Abacavir	ABC	NRTI	(4.5 – 6.5) ^a
Lamivudine	3TC	NRTI	3.5 ^a
Didanosine	ddl	NRTI	(1.3 – 2.2) ^a
Stavudine	d4T	NRTI	1.7 ^a
Zidovudine	AZT (ZDV)	NRTI	1.9
Emtricitabine	FTC	NRTI	3.5
Tenofovir	TDF	NRTI	(1.4 – 4) ^a
Delavirdine	DLV	NNRTI	6.2
Efavirenz	EFV	NNRTI	3
Nevirapine	NVP	NNRTI	4.5
Etravirine	ETR	NNRTI	(2.9-10) ^a
Rilpivirine	RPV	NNRTI	2.0
Doravirine	DOR	NNRTI	3.0
Fosamprenavir/r	FPV/r	PI	(4-11) ^a
Atazanavir	ATV	PI	2.2 ^a
Atazanavir/r	ATV/r	PI	5.2 ^a
Indinavir/r	IDV/r	PI	10 ^a
Lopinavir/r	LPV/r	PI	(9 – 55) ^a
Nelfinavir	NFV	PI	3.6
Saquinavir/r	SQV/r	PI	(2.3 – 12) ^a
Tipranavir/r	TPV/r	PI	(2 – 8) ^a
Darunavir/r	DRV/r	PI	(10 – 90) ^a
Ritonavir	RTV	PI	2.5
Enfuvirtide	T20	FI	6.48
Cabotegravir	CAB	INI	2.5
Raltegravir	RAL	INI	1.5
Elvitegravir	EVG	INI	2.5
Dolutegravir	DTG	INI	(4-13) ^a
Bictegravir	BIC	INI	(2.5- 10)

a. clinical cutoff (lower cutoff – higher cutoff).

- Phenotypic susceptibility to each drug in a subject's background regimen will be determined by applying drug-associated cutoffs as defined by the PhenoSense algorithm to the phenotypic fold resistance to that drug at a certain timepoint (e.g. Screening or Baseline).

Full Sensitivity

Fold Change	Interpretation
> clinical lower cutoff or biologic cutoff	resistance
≤ clinical lower cutoff or biologic cutoff	sensitive

Partial Sensitivity

Fold Change	Interpretation
> clinical higher cutoff	resistance
≤ clinical higher cutoff and > clinical lower cutoff	partially sensitive
≤ clinical lower cutoff	sensitive

Genotypic and Net Assessment Susceptibility

Genotypic and Net assessment susceptibility to all licensed antiretroviral drugs and CAB will be determined from Monogram Inc. Net assessment susceptibility will be reported with the categories of 'resistant', 'partially sensitive', and 'sensitive' as what will be performed for phenotypic susceptibility. Genotypic susceptibility will be reported with the categories of 'resistant', 'resistance possible' and 'sensitive'. Genotypic and Net assessment susceptibility will be assessed at time of CVF using plasma sample, Genotypic susceptibility may be assessed at baseline using PBMC.

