Long QT syndrome congenital																							
Torsade de pointes																							
Ventricular tachycardia																							
Cardiac arrest																							
Cardiac death																							
Cardiac fibrillation																							
Cardio-respiratory arrest																							
Electrocardiogram repolarisation abnormality																							
Electrocardiogram U wave inversion																							
Electrocardiogram U wave present																							
Electrocardiogram U-wave abnormality																							
Loss of consciousness																							
Sudden cardiac death																							
Sudden death																							
Syncope																							
Ventricular arrhythmia																							
Ventricular fibrillation																							
Ventricular flutter																							
Ventricular tachyarrhythmia																							
Laboratory Parameters																							

 If a laboratory value which is expected to have a numeric value for summary purposes, has a non-detectable level reported in the database, where the numeric value is missing, but typically a character value starting with '<x' or '>x' (or indicated as less than x or greater than x in the comment field) is present, the number of significant digits in the observed values will 																							

be used to determine how much to add or subtract in order to impute the corresponding numeric value. If a character value starting with “<=x”, then the numeric value will be x.

- Example 1: 2 Significant Digits = ‘< x’ becomes x – 0.01
- Example 2: 1 Significant Digit = ‘> x’ or ‘>=x’ becomes x + 0.1
- Example 3: 0 Significant Digits = ‘< x’ becomes x – 1

Estimate of Glomerular Filtration Rate (GFR) (Levey, 2012)

- Chronic Kidney Disease Epidemiology Collaboration (CKD-EPI) equation [Levey, 2012]. be used by the central laboratory to provide an estimate of GFR, in mL/min per 1.73 m², as follows:

$$GFR = 141 \times \min\left(\frac{CRT_{mg/dL}}{\kappa}, 1\right)^\alpha \times \max\left(\frac{CRT_{mg/dL}}{\kappa}, 1\right)^{-1.209} \times 0.993^{Age} \times [1.018 \text{ if Female}] \times [1.159 \text{ if Black}]$$

Abbreviations / Units:

eGFR (estimated glomerular filtration rate) = mL/min/1.73 m²

age = years at time of assessment

κ = 0.7 (if female) or 0.9 (if male)

α = -0.329 (if female) and -0.411 (if male)

min() = the minimum of CRT/κ or 1

max() = the maximum of CRT/κ or 1

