16.15.10. Virology Tables

Q2M vs. BIK only for virology tables in this section. Note no summary tables will be produced if less than 5 CVFs in total are observed (excluding subjects from site PPD). All planned listings will be produced regardless.

Note analysis population below has been updated to reflect the M12 analysis plan. No tables were produced at the M6 analysis (total number of CVFs <5).

Virology: Tables					
No.	Population	GSK Standard / Example Shell	Title	Programming Notes	Deliverable [Priority]
Genotypic					
7.1.	mCVF	207966/primary_15/T7.1	Summary of the Prevalence of Known INI Resistance Mutations at time of CVF (Maintenance Phase) – Plasma Sample		M6, M12
7.2.	mCVF	207966/primary_15/T7.2	Summary of the Prevalence of Major Resistance Mutations of NRTI, NNRTI and PI Class at time of CVF (Maintenance Phase) - Plasma Sample		M6, M12
7.3.	mCVF	207966/primary_15/T7.3	Summary of Genotypic Susceptibility at time of CVF (Maintenance Phase) - Plasma Sample		M6, M12
Phenotypic					
7.4.	mCVF	207966/primary_15/T7.4	Summary of Phenotype Susceptibility at Time of CVF (Maintenance Phase) - Plasma Sample		M6, M12

Virology: Tables					
No.	Population	GSK Standard / Example Shell	Title	Programming Notes	Deliverable [Priority]
7.5.	mCVF	207966/primary_15/T7.5	Summary of Phenotype: Number of Drugs to Which Subject is Phenotypic Resistant, Partially Sensitive or Sensitive at Time of CVF (Maintenance Phase) - Plasma Sample		M6, M12
7.6.	mCVF	207966/primary_15/T7.6	Summary of Fold Change to CAB, RPV and BIC at Time of CVF (Maintenance Phase) - Plasma Sample		M6, M12
Other					
7.7.	mCVF	207966/primary_15/T7.7	Summary of Net Assessment at Time of CVF (Maintenance Phase) - Plasma Sample		M6, M12

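### Fold-change results above the assay ceiling are set to the smallest ceiling in the study while measured values above it are not capped, so Table 7.6 can understate and mis-order high-level resistance

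*SAP*

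**What the plan says.** Section 16.6.7 gives its reason first: "Since the maximum assay limit for FC for each ART varies from assay to assay". It then takes results of the form "FC values that are greater than the maximum assay limit (e.g., '>100" (the example is a right-censored value) and states that each "will be interpreted as having a value equal to the smallest maximum assay limit for that ART in the study population for data analysis". Two further statements limit the reach of the rule. For listings, "Censored values will be presented 'as is' in the listings". For the categorical result, which comes from the vendor's dataset, "phenotypic susceptibility (i.e. full sensitivity and partial sensitivity) will not be re-derived in our analysis".

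The numeric fold change feeds one planned table, Table 7.6 in section 16.15.10: "Summary of Fold Change to CAB, RPV and BIC at Time of CVF (Maintenance Phase) - Plasma Sample". It is run on the modified confirmed virologic failure (mCVF) population. The same section adds that "no summary tables will be produced if less than 5 CVFs in total are observed", not counting the excluded site.

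The SAP lists no assay ceiling for any drug. It also says nothing about a measured result that is above the smallest ceiling but within its own assay's range.

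**The concern.** A common ceiling keeps values in order only if it is applied to every value above it. Here it is applied to censored values alone. A measured result cannot exceed the limit of the assay that produced it, so the rule never reaches it, and no other sentence does. The feature that motivates the rule, ceilings that vary, is also the condition under which it fails. With a single ceiling per drug there would be no inversion, and no need to choose the smallest.

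The SAP's general laboratory convention in section 16.6.4 behaves differently: "Example 2: 1 Significant Digit = ‘> x’ or ‘>=x’ becomes x + 0.1". That places a censored value just above its own limit, and so above anything measurable in that assay. The phenotype rule can place it below.

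At stake is the description of how resistant the virus was at failure to CAB, RPV and BIC. The table may rest on as few as five participants, so one misplaced value can move a summary statistic. The error in a censored value always runs towards lower apparent resistance.

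**Working it through.** There is no stated figure to reproduce, so the check applies the written rule to example records.

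**Inputs from the SAP (section 16.6.7).** Ceilings differ between assays; a censored result is replaced by the smallest ceiling for that drug; measured results have no rule.

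**Assumed inputs.** All ceilings and all fold-change values below are assumptions. The SAP's only number of this kind is the example '>100'.

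**Step 1: understatement of one censored result.** Let m be the smallest ceiling for a drug and L the ceiling of the assay that returned '>L'. The true value exceeds L and is analysed as m, so it is understated by a factor of at least L/m. With m = 100:

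| L | Understated by at least |
|---|---|
| 110 | 110/100 = 1.1 |
| 150 | 150/100 = 1.5 |
| 200 | 200/100 = 2.0 |
| 300 | 300/100 = 3.0 |

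If L = m, the result sits at its own ceiling and this rule adds nothing.

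**Step 2: condition for a reversal.** A measured value v and a censored '>L' for the same drug are provably reversed when v is above m and at or below L. The true order is then v below '>L', while the analysed order is m below v. Differing ceilings alone are not enough. With a measured 130 and a '>100', the true order is unknown and no reversal is shown.

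**Step 3: five records for one drug, smallest ceiling 100.** Records: 130 (measured in the assay with ceiling 200), '>200', 45, '>100', 8.

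| Rule | Values analysed | Sum | Mean | Median | Maximum |
|---|---|---|---|---|---|
| As written | 130, 100, 45, 100, 8 | 383 | 76.6 | 100 | 130 |
| Cap every value at 100 | 100, 100, 45, 100, 8 | 353 | 70.6 | 100 | 100 |
| Own ceiling | 130, 200, 45, 100, 8 | 483 | 96.6 | 100 | 200 |

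As written, the '>200' virus enters at 100, below the one measured at 130, and the maximum belongs to the wrong participant. The median is unchanged here, but in the own-ceiling row it falls on a censored record. The true middle value lies above 100 and no higher than 130, so it should be shown as '>100'.

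**Step 4: a second set, where the median moves.** Records: 1.2, 3.0, 120 (measured), '>150', '>200', smallest ceiling 100.

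| Rule | Values analysed | Median | Geometric mean | Maximum |
|---|---|---|---|---|
| As written | 1.2, 3.0, 120, 100, 100 | 100 | 21.2 | 120 |
| Cap every value at 100 | 1.2, 3.0, 100, 100, 100 | 100 | 20.5 | 100 |
| Own ceiling | 1.2, 3.0, 120, 150, 200 | 120 | 26.5 | 200 |

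Both sets show the same pattern. Capping everything removes the reversal by creating ties, but it lowers the mean (arithmetic or geometric) and the maximum further. Only the own-ceiling rule limits the understatement.

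**The case against.** The sponsor could reply that a common ceiling was intended for all values and that no programmer would leave measured ones uncapped. That may be the intent, but the text does not say it. The quoted example and the later reference to censored values both confine the rule to over-limit results. Read literally, it produces the reversal; read by intent, a different table results.

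The stronger reply is that little follows from it, and most of that reply stands:

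- The assay ceilings are assumed. Nothing in the SAP shows that records such as those above are typical or expected.
- The layout of Table 7.6 rests on a table from another study, and the mock shells are available only on request. Which statistics it will contain is therefore not known from this document.
- Listings show the censored value unaltered, and Listing 64 covers every participant with confirmed virologic failure. With few failures, a reader could see a '>200' directly.
- No virology tables were produced at Month 6, because there were fewer than five failures.

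A reader might also infer that the secondary endpoint on treatment-emergent resistance is biased. The documents do not support that. Section 2.2 defines the endpoint as an incidence, which counts participants and does not average fold change, and the susceptibility categories are the vendor's. The cutoffs in section 16.6.7 are 2.5 for CAB, 2.0 for RPV and 2.5 to 10 for BIC, so on the assumed ceilings every affected virus is above its cutoff either way.

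**Conclusion.** The rule as written is faulty, but its reach is small. It sets a ceiling for censored results only. Wherever ceilings for one drug differ, a censored result from a higher-ceiling assay is understated by at least L/m. Where a measured value also lies between the two ceilings, the order is reversed and the maximum can belong to the less resistant virus.

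It would go too far to say that a reversal occurs whenever ceilings differ and some measured value exceeds the smallest. It also needs a censored result for the same drug whose own ceiling is at or above that measured value.

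The conclusion rests on the SAP's statement that ceilings vary and on the literal reading that measured values stay as measured. The factors of 1.1 to 3.0 and both sets of records are illustrations. The effect is confined to the descriptive summary in Table 7.6, and only if it is produced. Listings, vendor susceptibility categories, and the primary and key secondary analyses are unaffected. This is a worthwhile correction of low severity.

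**What to change.** In section 16.6.7, replace the substitution rule with one sentence: each censored fold-change result is kept at its own assay ceiling; fold change is summarised by median and range with the '>' sign shown wherever the reported statistic is a censored value; and the number of censored results is given by drug and arm. This still cannot order a '>100' against a measured 130, which is why the sign and the count should be displayed and a mean avoided.

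If a common ceiling is preferred, apply it to every value, measured and censored, and display those at the ceiling as '>=limit'. The text should then note that this restores consistent ordering, with ties, but does not reduce the understatement of high-level resistance.

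The cost is one sentence in section 16.6.7 and a small change to the derivation and display for Table 7.6. No new data are needed.
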